14. IMMUNOGENICITY ASSESSMENTS

A validated immunoassay will be used to assay samples for the presence of, and measure titers of, anti-BIIB092 antibodies in serum on an ongoing basis in Study 251PP301. Samples will be collected during the 52-week double-blind period at Day 1, Week 4, Week 8, Week 12, Week 24, Week 36, and Week 48 (Table 2). In addition, samples will also be collected during the open-label extension period approximately every 24 weeks (Table 3). All samples will be collected predose.

Anti-drug antibody (ADA) titers will be monitored throughout the course of Study 251PP301. If ADAs are observed, analyses will be conducted to assess impacts on safety, pharmacological, and efficacy measures across treated participants with and without ADAs. ADAs may also be assessed for neutralizing activity.

Participants who withdraw from Study 251PP301 with ADA titers that are not stable or are increasing in two consecutive samples leading up to discontinuation will be asked to return for follow-up assessment approximately every 6 weeks for up to 24 weeks for measurement of ADAs and immunological AE assessment until resolved (defined as two sequential samples showing no change or declining levels).

Clinically relevant immune reactions (e.g., hypersensitivity reactions) will be treated according to current standard of care medical practice. Additional samples for immunogenicity assessments referred to as “event driven” samples may be justified on the basis of \geq Grade 3 hypersensitivity reactions. The immunogenicity and corresponding drug exposure (PK) data from these samples will be reported as part of a participant’s overall PK and immunogenicity assessment.

CONFIDENTIAL

The information contained herein may not be used, disclosed, or published without the written consent of
Biogen MA Inc.

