3 GENERAL CONSIDERATIONS

3.1 General Methods

This statistical analysis plan (SAP) is for the purpose of the interim analysis which will use data collected in the placebo-controlled (PC) and open label extension (OLE) periods once all subjects have completed the PC period. It covers the analyses for the OLE portion of the study and analyses across both the PC and the OLE periods. The analysis for the PC period is documented in a separate 251PP301 placebo-controlled SAP. The analyses of selected exploratory endpoints may be documented separately. Since the objectives and endpoints given in Section 2 are taken directly from the protocol which covers both PC and OLE periods, only analyses relevant to the OLE

period which will have sufficient data at the time of the interim analysis will be presented in this SAP.

Summary tables will be presented using descriptive summary statistics. For continuous variables, summary statistics will generally include: number of subjects with data, mean, standard deviation, median, 25% percentile, 75% percentile, minimum and maximum. For categorical variables, this will generally include: number of subjects randomized or dosed, number with data, and the percent of those with data in each category.

Unless otherwise specified, change from baseline will be defined as post-baseline value minus baseline value. See Section 3.3 for the definition of baseline.

Unless stated otherwise, all statistical tests will be 2-sided with statistical significance level of 0.05.

The statistical software, SAS® will be used for all summaries and analyses.

The health care region used in the analysis (referred as region in this SAP) is defined as:

- US: United States
- Non-US: Australia, Austria, Canada, France, Germany, Greece, Italy, Russian, Spain, United Kingdom, Japan and Korea

The term “subject” is the equivalent to “participant” used in the protocol.

This OLE period analysis plan does not include listings since they are provided in the placebo-controlled period analysis (please refer to the 251PP301 placebo-controlled SAP). These listings will include all data in the placebo-controlled and OLE periods (all data in the study), with an indicator of the study period (screening, placebo-controlled, or OLE) for each record to indicate when the event occurred.

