6 SAFETY DATA

6.1 General Considerations

6.1.1 Analysis population

Safety population will be used for safety analyses of AEs, clinical laboratory data, [REDACTED] data, ECG data, and vital signs data. The safety MRI population will be used for the analysis of safety MRI data.

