6.2.4 Adverse event of special interest

Immunogenicity is an AESI in the BIIB092 clinical development program. Adverse events representing potential immune/hypersensitivity reactions will be identified using customized MedDRA search criteria: Anaphylactic reaction, Angioedema, and Severe cutaneous adverse reactions via SMQ (narrow and broad) search; Eosinophilia, and Miscellaneous terms. Further details are given in Appendix 11.1.

An incidence proportion table for potential immune/hypersensitivity reactions organized by SMQ/Miscellaneous categories and by PT (for both AEs and SAEs), and similarly for potential immune/hypersensitivity reactions for subjects with and without treatment emergent positive anti-drug antibody (ADA) results will be presented for both AEs and SAEs for the OLE Period. Positive treatment emergent ADA will be based on the definition in Section 8 using the integrated placebo-controlled and open label extension data.

An exposure adjusted incident rate table will be provided for the active treatment (placebo-controlled and OLE) period.

The following analyses (incidence proportion only) will be performed for the OLE period to explore the relationship between ADAs and the safety of BIIB092:

- AEs for subjects with and without positive treatment emergent ADAs
- SAEs for subjects with and without positive treatment emergent ADAs

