8 ANTI-DRUG ANTIBODY DATA

Analyses for anti-drug antibodies (ADAs) will be based on subjects in the ADA population, defined as subjects in the safety population who had at least one post-dose evaluation for ADAs.

Active treatment period baseline will be used for ADA. If baseline is missing then it will be imputed as negative.

The following definitions will be used in the analysis of ADA data:

- Treatment emergent positive:
 - A post-baseline subject sample that is positive when the baseline sample is negative; or
 - A post-baseline subject sample that has a titer greater than or equal to 4 times the baseline sample titer when the baseline sample is positive. If the titer value is not available for a positive baseline result, then the baseline titer value will be imputed as the minimum required dilution (MRD); or
 - A positive post-baseline result where no titer is available, regardless of baseline value
- Persistently positive: Two or more treatment emergent positive ADA results, where the time between the first and last positive results is 16 weeks or more; or if there are no further samples available 16 weeks or more following a treatment emergent positive result (including the OLE period).
- Transiently positive: more than one treatment-emergent positive evaluation, less than 16 weeks apart, or a single treatment emergent positive (not including pretreatment) when there are samples available 16 weeks or more following the positive result.

The number and percentage of subjects with any sample that tested positive in the ADA assay (including at baseline), and the number and percentage of subjects without any positive post-treatment result (regardless of baseline) will be presented. The number of subjects with treatment emergent positive at each visit and at any time post-baseline will be presented; the number and percentage of subjects with persistently positive response and subjects with transiently positive responses will be presented similarly.

In this study, additional samples for ADA, referred to as “event driven” samples, may be collected for subjects with hypersensitivity events. Data from these samples will be considered part of a subject’s overall ADA assessment.

Associations of ADA with PK and/or select AEs may be explored.

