6.2.3 Adverse event of special interest

Immunogenicity is an AESI in the BIIB092 clinical development program. Adverse events representing potential immune/hypersensitivity reactions will be identified using customized MedDRA search criteria: Anaphylactic reaction, Angioedema, and Severe cutaneous adverse reactions via SMQ (narrow and broad) search; Eosinophilia, and Miscellaneous terms. Further details are given in Appendix 11.3.

An incidence proportion table for potential immune/hypersensitivity reactions organized by SMQ/Miscellaneous categories and by PT (for both AEs and SAEs), and similarly for potential immune/hypersensitivity reactions for subjects with and without treatment emergent positive anti-drug antibody (ADA) results (as defined in Section 8) will be presented for both AEs and SAEs. A listing of potential immune/hypersensitivity reactions will be provided.

The following analyses (incidence proportion only) will be performed to explore the relationship between ADAs and the safety of BIIB092:

- AEs for subjects with and without treatment emergent positive ADAs
- SAEs for subjects with and without treatment emergent positive ADAs

In this study, additional samples for ADA, referred to as “event driven” samples, may be collected for subjects with hypersensitivity events. A listing of AEs for subjects with any event driven ADA samples will be provided.

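### The OLE tables of adverse events by ADA status have no category for late-start subjects never tested on BIIB092; by default these count as without ADA, which can distort the comparison

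*SAP*

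**What the plan says.** Immunogenicity is the programme's adverse event of special interest. OLE SAP Section 6.2.4 states: "The following analyses (incidence proportion only) will be performed for the OLE period to explore the relationship between ADAs and the safety of BIIB092". The first table listed is "AEs for subjects with and without positive treatment emergent ADAs", followed by the same for SAEs. The section splits potential immune/hypersensitivity reactions by ADA status too, and Section 6.2.5 (OLE tables 3 and 4) does so for infusion reactions and serious infusion reactions. On grouping: "Positive treatment emergent ADA will be based on the definition in Section 8 using the integrated placebo-controlled and open label extension data".

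Neither section names a population for the split tables. Three other places bear on it:

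- Section 6.1.1: "Safety population will be used for safety analyses of AEs, clinical laboratory data".
- The Analysis Period part of Section 3 reads this, for the OLE adverse event incidence table, as every randomized subject dosed in the OLE. It sets no ADA-sample condition.
- Section 8 bases ADA analyses on an ADA population, namely "subjects in the safety population who had at least one post-dose evaluation for ADAs". It imputes a missing baseline as negative and has no rule for a missing post-baseline result.

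On sampling, Protocol Section 14 says "samples will also be collected during the open-label extension period approximately every 24 weeks". Protocol Table 3 puts the first of these at Week 76 and marks none at the OLE Early Discontinuation visit. Late-start subjects get their first BIIB092 dose at Week 52 (Protocol Section 5.1.1).

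On timing, the OLE SAP serves an interim analysis of data from the placebo-controlled and OLE "periods once all subjects have completed the PC period" (Section 3.1). Section 5.3 expects too few subjects at Week 100 to support the MRI and CSF analyses.

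The placebo-controlled (PC) SAP has a counterpart table in Section 6.2.3, "AEs for subjects with and without treatment emergent positive ADAs".

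**The concern.** A two-way split needs a rule for subjects whose status is unknown, and there is none here. A late-start subject with under 24 weeks of OLE at the lock, and no event-driven sample, has no ADA result on BIIB092. Such a subject cannot be positive, so a programmer following the text would place them in the without group.

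That group then combines subjects who tested negative with subjects who have short exposure and no test. Because the tables give unadjusted proportions, exposure time feeds straight into the comparison. The SAP recognises this problem elsewhere: Section 6.2.3 uses follow-up-adjusted rates because the active-treatment period differs in length between early and late start. No such adjustment is specified by ADA status. These tables are the plan's main look at whether ADA goes with harm, so a bias there matters even if its direction is uncertain.

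**Working it through.** **Plan's own figures.** At 25% dropout, 306 × 0.75 = 229.5 (plan: 230), 153 × 0.75 = 114.75 (plan: 115) and 459 × 0.75 = 344.25 (plan: 345). I use 230 early-start and 115 late-start subjects, which are upper bounds on OLE entrants.

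**Assumed inputs, not in the documents.** OLE follow-up at the lock is uniform on 0 to F weeks, with F = 40, 52 or 65. The event rate λ is 0.4, 1.0 or 2.0 per subject-year. ADA positivity is 5%, 10% or 20% of tested subjects in both groups, with no true link to events. All early-start subjects count as tested, because they are sampled from Week 4 of the PC period. The Section 5.3 remark favours the smaller F: the share past Week 100 (48 OLE weeks) is 0% at F = 40, 4/52 = 8% at F = 52 and 17/65 = 26% at F = 65.

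**Untested share of late start.** u = 24/F, giving 60% (69 of 115), 46% (53) and 37% (about 42).

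**Expected proportion with an event**, for follow-up uniform from a to b weeks:

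1 − [52 / (λ(b − a))] × [exp(−λa/52) − exp(−λb/52)]

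**Worked case: F = 52, λ = 1, ADA 10%.**

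- Early start (0 to 52 weeks): 1 − (1 − 0.368) = 0.368.
- Late start, tested (24 to 52): 1 − (0.630 − 0.368)/0.538 = 0.513.
- Late start, untested (0 to 24): 1 − (1 − 0.630)/0.462 = 0.199.
- Counts: early start 23 with and 207 without; late start tested 61.9, of whom 6.2 with and 55.7 without; late start untested 53.1.

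Late-start column: with 0.513; without (55.7 × 0.513 + 53.1 × 0.199)/108.8 = 0.360; ratio 1.43.

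Total column: with (23 × 0.368 + 6.2 × 0.513)/29.2 = 0.399; without (207 × 0.368 + 55.7 × 0.513 + 53.1 × 0.199)/315.8 = 0.365; ratio 1.09.

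Untested removed: late start 0.513/0.513 = 1.00. In the total column, without becomes (207 × 0.368 + 55.7 × 0.513)/262.7 = 0.399, ratio 1.00.

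**Range over all assumed rates, no true effect.**

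| F (weeks) | Late-start ratio | Total ratio |
|---|---|---|
| 40 | 1.45–1.64 | 1.08–1.11 |
| 52 | 1.35–1.51 | 1.07–1.11 |
| 65 | 1.28–1.42 | 1.07–1.10 |

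The early-start column has no untested subjects under these assumptions, so its ratio is 1.00.

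**Events that cluster early (F = 52, ADA 10%).** Suppose a late-start subject has a 20% risk, all within the first 12 weeks on BIIB092. Half the untested are past 12 weeks and the rest have on average half the window behind them, so their risk is 0.75 × 0.20 = 0.15. The late-start ratio is 0.20 / [(55.7 × 0.20 + 53.1 × 0.15)/108.8] = 1.14. The total ratio is 0.88, 0.96, 1.01 or 1.04 if the early-start OLE risk is 5%, 10%, 15% or 20%.

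**True hazard ratio of 2 (F = 52; λ 0.4 or 1.0; ADA 10% or 20%).** The total-column ratio is 1.65–1.93 with the untested in the without group and 1.52–1.76 among tested subjects only.

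**The case against.** The strongest reply is that Section 8 is the specific rule. It assigns ADA analyses to the ADA population and mentions ADA–AE associations, and Section 6.2.4 refers to it for ADA status. The Analysis Period text also says population and period together decide who is included, so an ADA population for the OLE could be read as requiring an OLE sample. This stands to the extent that the safety population is inferred for these tables, not stated. It does not clearly cure the gap. The only period examples given are for the safety population. As worded, post-dose can be met by a sample taken on placebo, because the safety population counts placebo as study treatment. The active-treatment baseline in Section 8 then stops that same sample from making a late-start subject treatment-emergent positive.

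Three further limits hold:

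- The 24-week wait applies only to scheduled samples in late-start subjects. Event-driven samples after Grade 3 or higher hypersensitivity count toward ADA status, so some early reactors will be tested. That is also a selection, since subjects without such an event are not sampled early.
- Subjects who stop treatment but stay enrolled are still expected at Week 76, so stopping early does not by itself mean untested.
- Counts are small. In the worked case there are 6.2 ADA-positive late-start subjects, of whom 6.2 × 0.513 = 3.2 would have an event. For an event at 0.10 per year over their mean 38 weeks, it is 6.2 × [1 − exp(−0.10 × 38/52)] = 0.4. The AE and SAE analyses are described as exploratory.

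A reader might infer that the plan will manufacture a false link between ADA and harm, or that late start as a whole has shorter OLE follow-up. The documents support neither. Both groups enter the OLE at Week 52, and only the untested late-start subjects have short follow-up. The total column moves little and can move the other way.

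**Conclusion.** The gap is real and should be closed before the tables are programmed. The split tables have neither a named population nor a category for subjects untested on BIIB092. Under the default population, and not clearly avoided under the ADA population, those subjects enter the without group.

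With no true effect and a constant hazard, the distortion is about 1.3 to 1.6 in the late-start column and 1.07 to 1.11 in the total column. There is none from this mechanism in the early-start column. The total column can reverse if events cluster early. All these sizes rest on assumed follow-up, event rates and ADA rates, with no OLE dropout modelled. The return to 1.00 among tested subjects also relies on a flat chance of positivity. In practice longer follow-up brings both more ADA samples and more events, so restriction alone does not make the groups comparable.

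The PC SAP version is minor: it concerns only subjects who leave before the Week 4 sample. This is a question of table population, not of clinical management.

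**What to change.** - OLE SAP 6.2.4 and 6.2.5: limit the with/without ADA tables to subjects with at least one evaluable ADA sample after their first BIIB092 dose, and show the remaining dosed subjects in a separate not-tested column.
- OLE SAP 3.2 (Population) and 8: for OLE and active-treatment analyses, define post-dose as after the first BIIB092 dose.
- OLE SAP 6.2.4 and 6.2.5: add exposure-adjusted rates by ADA status, to deal with the unequal follow-up that restriction leaves.
- PC SAP 6.2.3: add the same not-tested column for subjects with no sample after their first study dose.

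The cost is SAP wording, one column and the added rate tables. No new data are needed. The downside is smaller denominators in the late-start column.

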6.2.5 Infusion reactions

Infusion reactions will be identified through 1) temporal association, defined as those events which occur on the day of an infusion or the subsequent two calendar days after an infusion; and 2) through a custom MedDRA search of preferred terms. The list of custom MedDRA search terms can be found in Appendix 11.2. A serious infusion reaction is a serious adverse event which is identified by one or both methods.

For the OLE period, an overall summary of infusion reactions will be provided with the number of subjects (n, %) with any infusion reaction; with any infusion reaction identified by temporal association only; with any infusion reaction identified through the custom search only; and any infusion reaction identified through both methods. Additionally, the following incidence proportion tables will be provided for the OLE period:

1. Infusion reactions (temporal association or custom search) by SOC and PT
2. Serious infusion reactions (temporal association or custom search) by SOC and PT
3. Infusion reactions (temporal association or custom search) for subjects with and without positive treatment emergent ADAs by PT
4. Serious infusion reactions (temporal association or custom search) for subjects with and without positive treatment emergent ADAs by PT
5. Infusion reactions that occurred in temporal association to an infusion by physical location of infusion (in-clinic vs. home) by SOC and PT
6. Serious infusion reactions that occurred in temporal association to an infusion by physical location of infusion (in-clinic vs. home) by SOC and PT
7. Infusion reactions identified through custom search criteria by PT
8. Infusion reactions (temporal association or custom search) by 12-week intervals by PT

Positive treatment emergent ADA will be based on the definition in Section 8 using the integrated placebo-controlled and open label extension data.

An exposure adjusted incident rate table for infusion reactions will be provided for the active treatment (placebo-controlled and OLE) period.

Additionally, the following incidence proportion tables will be provided for the active treatment (placebo-controlled and OLE) period:

1. Infusion reactions that occurred in temporal association to an infusion by physical location of infusion (in-clinic vs. home) by SOC and PT
2. Serious infusion reactions that occurred in temporal association to an infusion by physical location of infusion (in-clinic vs. home) by SOC and PT

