5.1.1. Overall Study Design

The study design schematic is presented in [Figure 1](#). The study will consist of a 52-week double-blind treatment period, which will be followed by a long-term open-label extension period for follow up. Participants will be randomized to receive BIIB092 or placebo. Approximately 459 participants in total will be randomized in a 2:1 ratio to receive BIIB092 or placebo (306 participants active or 153 placebo). In the double-blind treatment period of the study, participants will be dosed approximately once every 4 weeks (Q4W) up to a total of 13 times, with the last dose of study treatment of the double-blind period (Dose 13) administered at Week 48.

At Week 52, participants completing the double-blind treatment period may choose to continue into the open-label extension period of the study. Participants who wish to continue in the open-label extension period will receive the first dose of the open-label study treatment at Week 52. Participants will be dosed approximately once Q4W throughout the duration of the open-label extension period. The duration of the open-label extension period will vary depending on the date of enrollment of the participant in the study. The study is expected to continue until BIIB092 is commercially available, the development program is terminated, or the study is terminated at the discretion of the Sponsor, whichever comes first.

CONFIDENTIAL

The information contained herein may not be used, disclosed, or published without the written consent of Biogen MA Inc.

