5.1.4. Home Visits

After Week 24, except for those visits when clinical scales, LPs, or MRI assessments are performed, visits and procedures may be performed in the home as long as appropriate services

CONFIDENTIAL

The information contained herein may not be used, disclosed, or published without the written consent of Biogen MA Inc.

are available to perform the required study procedures and adequately monitor for potential safety events. In the double-blind period of the study, Weeks 28, 32, 40, and 44 may qualify for home visits.

In the open-label extension period of the study, Week 68, 72, 80, 84, 92, 96, 104, 108, 116, 120, 128, 132, 140, 144, 152, 156, 164, 168, 176, 180, 188, and 192 visits may qualify for a home visit. However, in the event that the participant experienced a clinically significant infusion reaction during the first 24 weeks of the protocol, the participant should not be administered BIIB092 in the home unless previously approved by the Study Investigator.

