4.3 Study Drug Exposure and Study Drug Compliance

A summary table of study drug exposure and compliance in the OLE period will be provided. Number of doses (BIIB092) received will be summarized as a categorical variable (categories of 1-5, 6-10, 11-15, 16-20, 21-26, 27-39, 40-52 and 53-65) as well as a continuous variable. The number of doses (BIIB092) received via home infusion will be summarized. Number of weeks on study treatment (BIIB092), calculated as (date of last dose – date of first dose +28)/7, will be summarized as a categorical variable (every 6 months for the first 2 years of OLE, and then every year) as well as a continuous variable. Percentage of study treatment taken up to the last dose, calculated as (the actual number of doses divided by the number of doses a subject is expected to take until the date of last dose)*100, will be summarized as a continuous variable. This table will be presented by OLE treatment group. A similar table will also be provided on the active treatment (PC and OLE) period in order to summarize the exposure data while subjects are on BIIB092.

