6.1.4 Incidence, incidence proportion and incidence rate

- Incidence and incidence proportion will be provided in incidence proportion tables. Incidence is defined as the number of subjects who experienced an event. Incidence proportion is defined as the number of subjects who experienced an event divided by total number of subjects in the analysis population, i.e., percentage. Each subject will be counted only once within each category.

- Incidence and incidence rate will be provided in incidence rate tables. Two different kinds of incidence rate tables will be provided as appropriate for different analyses. Definitions are provided below.
 - Follow-up adjusted incidence rate (FAIR) – defined as the number of subjects with an event divided by the total follow-up time among the subjects in the analysis population (e.g., incidence rate per 100 subject-years). The total follow-up time (subject-years) is the sum of all subjects' follow-up time, where a subject's follow-up time is calculated as the number of days (inclusive) from first dose of treatment until the last day on study divided by 365.25. For active treatment period analyses, the first dose of treatment is considered the first dose received in the study period (PC or OLE) in which a subject first receives BIIB092. Each subject will be counted only once within each category.
 - Exposure-adjusted incidence rate (EAIR) – defined as the number of subjects with an event divided by the total exposure adjusted follow-up time (i.e. total time at risk for the event) among the subjects in the analysis population (e.g., incidence rate per 100 subject-years). The exposure adjusted follow-up time (time at risk for the event) for a subject is the time from the first dose of study drug in the first BIIB092 dosing period (PC or OLE) to the initial occurrence of the event for subjects who experienced the event, and is the time from first dose of study drug in the first BIIB092 dosing period to the end of follow-up (the last day on study) for subjects who did not experience the event. The total time at risk is the sum of all subjects' time at risk. Each subject will be counted only once within each category.

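### Home and in-clinic infusion reactions are both tabulated over all subjects, so the two columns are not comparable even at equal risk per infusion

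*SAP*

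**What the plan says.** OLE SAP Section 6.2.5 lists, among its incidence proportion tables, "Infusion reactions that occurred in temporal association to an infusion by physical location of infusion (in-clinic vs. home) by SOC and PT". A matching table covers serious reactions, and both are repeated for the active treatment period, so there are four by-location tables. Section 6.1.4 fixes the general denominator: "Incidence proportion is defined as the number of subjects who experienced an event divided by total number of subjects in the analysis population". The population and analysis-period sections of the OLE SAP define no population by place of infusion.

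A reaction is temporally associated if it is among "those events which occur on the day of an infusion or the subsequent two calendar days after an infusion", so every infusion opens a new three-day window.

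One exposure-adjusted display is planned: "An exposure adjusted incident rate table for infusion reactions will be provided for the active treatment (placebo-controlled and OLE) period". It is not split by location. Section 4.3 adds that "The number of doses (BIIB092) received via home infusion will be summarized", but nothing links that count to the reaction tables.

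Protocol Section 5.1.4 makes home visits optional and lists where they may occur. "In the double-blind period of the study, Weeks 28, 32, 40, and 44 may qualify for home visits"; in the OLE they are "Week 68, 72, 80, 84, 92, 96, 104, 108, 116, 120, 128, 132, 140, 144, 152, 156, 164, 168, 176, 180, 188, and 192". The same section says that a participant with a clinically significant infusion reaction in the first 24 weeks should not be dosed at home unless the investigator has approved it.

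**The concern.** The number of subjects with at least one temporally associated reaction at a location grows with the number of infusions given there and with the number of subjects who received any there. Both differ between clinic and home by design: everyone starts in clinic, only some visits can move home, and only some participants will use them. Dividing both columns by the same total corrects for neither. Applied as written, a subject never infused at home counts as a reaction-free subject in the home column.

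Elsewhere the SAP accepts the need to adjust. Section 6.2.3 uses follow-up-adjusted rates because early and late starters have active treatment periods of different length. The by-location tables have a comparable imbalance and no adjustment. Someone reading the two columns side by side could take a difference in exposure for a difference in risk.

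**Working it through.** **Step 1: count the infusions.** The protocol gives dosing "once every 4 weeks (Q4W) up to a total of 13 times" in the double-blind period. Weeks 0 to 48 at four-week steps give 48/4 + 1 = 13, which reproduces that figure. Four of the 13 (Weeks 28, 32, 40, 44) may be at home and 9 are clinic only. In the OLE the first dose is at Week 52 and the first home-eligible visit is Week 68.

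Maximum home use per subject, OLE period:

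| OLE follow-up to | Infusions | Clinic | Home |
|---|---|---|---|
| Week 64 | 4 | 4 | 0 |
| Week 76 | 7 | 5 | 2 |
| Week 88 | 10 | 6 | 4 |
| Week 96 | 12 | 6 | 6 |
| Week 100 | 13 | 7 | 6 |
| Week 108 | 15 | 7 | 8 |
| Week 196 | 37 | 15 | 22 |

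Early starters followed to Week 100 in the active treatment period have 13 + 13 = 26 infusions: at most 4 + 6 = 10 at home, and at least 16 in clinic.

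**Step 2: formula.** Let p be the risk of a reaction per infusion, the same at both places and independent across infusions, and u the share of subjects who use every eligible home visit. Neither is in the documents; both are assumptions. With c clinic-only and h home-eligible infusions, the expected proportions of all subjects are:

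- clinic = u[1 − (1−p)^c] + (1−u)[1 − (1−p)^(c+h)]
- home = u[1 − (1−p)^h]

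**Step 3: early starters to Week 100, p = 1%.** Here 1 − 0.99^16 = 14.9%, 1 − 0.99^26 = 23.0% and 1 − 0.99^10 = 9.6%.

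- u = 10%: 22.2% against 0.96%, ratio 23.2.
- u = 30%: 0.3 × 14.9% + 0.7 × 23.0% = 20.6% in clinic; 0.3 × 9.6% = 2.9% at home; ratio about 7.
- u = 80%: 16.5% against 7.6%, ratio 2.2.

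**Step 4: OLE period, p = 2%, clinic against home.**

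| OLE follow-up to | u = 25% | u = 50% | u = 100% |
|---|---|---|---|
| Week 76 | 12.3% vs 1.0% | 11.4% vs 2.0% | 9.6% vs 4.0% |
| Week 100 | 20.6% vs 2.9% | 18.1% vs 5.7% | 13.2% vs 11.4% |
| Week 196 | 46.0% vs 9.0% | 39.4% vs 17.9% | 26.1% vs 35.9% |

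The only reversal is at full uptake with follow-up to Week 196; at 75% uptake that cut-off still gives 32.8% against 26.9%. With p at 1% or 5% the direction is the same in every cell.

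**Step 5: the same data per infusion.** Take 100 early starters to Week 100 with u = 30% and p = 1%. Clinic infusions number 30 × 16 + 70 × 26 = 2300, with 23 expected to be followed by a reaction. Home infusions number 30 × 10 = 300, with 3 expected. Both give 1.0 per 100 infusions, as equal risk should.

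**The case against.** The strongest reply is that the denominator is inferred. Section 6.1.4 is a general definition, and the same list in 6.2.5 includes tables for subjects with and without treatment-emergent antibodies, which make sense only with subset denominators. The programmer might therefore divide by subjects infused at each location. On that reading the Step 3 case at 30% uptake becomes 20.6% against 9.6%, a ratio of about 2.1 rather than 7. This stands as a caution about size. It does not rescue the tables: no such denominator is written down, and the imbalance in infusions per subject remains.

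A reader might infer that home infusion will look safer whatever happens. The documents do not support that. At full uptake the OLE counts are 6 and 6 at Week 96, home exceeds clinic from Week 108, and the bias can reverse. A reader might also take the tables as the trial's evidence on the safety of home infusion. No objective or endpoint concerns that question; these are descriptive displays with no test or decision rule.

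Part of the exposure is visible elsewhere: home doses are summarized, and the placebo-controlled SAP orders a listing of infusion reactions, with listings generally covering both periods. A reader could build a crude rate by hand. The planned tables would not show it, because each subject counts once per category.

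**Conclusion.** The point holds in a limited form. Followed as written, the by-location tables give columns that differ at equal risk per infusion. OLE SAP Section 5.3 says too few patients will have reached Week 100 at this database lock. Over that follow-up the schedule allows no more home than clinic infusions even at full uptake, so the bias here is towards home looking safer.

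The size is not fixed by the documents. It rests on uptake and on risk per infusion, both assumed: from a ratio of 23.2 at 10% uptake to 2.2 at 80% in the early-start illustration, and close to nothing for the OLE period to Week 100 at full uptake (13.2% against 11.4%). The 7-fold figure is one illustration, not a forecast. The change is worth making before the tables are programmed, because the displays are hard to interpret otherwise and the remedy is cheap.

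**What to change.** For the four by-location tables in OLE SAP Section 6.2.5:

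- Report infusions followed by a reaction per 100 infusions given at that location.
- Report subjects with a reaction divided by subjects with at least one infusion at that location.
- Show both denominators in the table.
- Add a comparison limited to home-eligible visits, setting clinic infusions at those visits against home infusions at the same visits. Restricting the clinic column to all visits after Week 24 would not be enough: late starters receive their first BIIB092 doses at Weeks 52 to 64, all in clinic. The restriction also leaves out the Week 52 and Week 100 visits, where lumbar puncture may add events within the window.
- Label the comparison as non-randomized. Participants with an early clinically significant reaction are largely kept out of home dosing, and no choice of denominator removes that selection.

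The cost is a small amount of extra programming. Home doses are already to be summarized under Section 4.3, so no new data are needed.
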